18.8.1.3 Conversions

Table 49 and Table 50 provide conversions to be performed in order to assess the CS dosage:

Table 49: Conversion factors in prednisone equivalent

Who-drug Term	Conversion factor in prednisone equivalent
METHYLPREDNISOLONE	1,25
METHYLPREDNISOLONE SODIUM / METHYLPREDNISOLONE SODIUM SUCCINATE	1,25
METHYLPREDNISOLONE ACETATE	1,25
HYDROCORTISONE / HYDROCORTISONE SODIUM SUCCINATE	0,25
BETAMETHASONE	8.333
BETAMETHASONE DIPROPIONATE	8.333
BETAMETHASONE VALERATE	8.333
BETAMETHASONE PHOSPHATE	8.333
DEXAMETHASONE	6,667
TRIAMCINOLONE / TRIAMCINOLONE ACETONIDE	1,25
CORTISONE	0,2
PREDNISOLONE	1
PREDNISONE	1
DEFLAZACORT	0,83333
MEPREDNISONE	1,25
PARAMETHASONE	2,5
CRONOLEVEL	8,333
BETROSPAM	8,333

Table 50: Frequency conversions for CS

Frequency	Conversion factor	Numerical Conversion factor
OAM	1/30	0,0333
QOD	1/2	0,5000
QW	1/7	0,1429
QWK	1/7	0,1429
BID/Q12	2	2,0000
TID/Q8	3	3,0000
QD – including QD with AM or PM (e.g. QD(AM), QD(PM), QD at AM, QD at PM)	1	1,0000
ONCE	1	1,0000
QAM	1	1,0000
Q2H	12	12,0000
Q3H	8	8,0000
Q4H	6	6,0000
Q6H	4	4,0000
Q8H	3	3,0000
Q12H	2	2,0000
QHS	1	1,0000
QID/Q6	4	4,0000
QPM	1	1,0000
QH	24	24,0000
Q3W	1/21	0,0476
TIW or Three times a week	3/7	0,4286
Four times a week	4/7	0,5714
Q4W	1/28	0,0357
BIW or Twice a week	2/7	0,2857
EVERY 3 HOURS	8	8,0000
X1	1	1,0000
EVERY OTHER DAY	1/2	0,5000
EVERY OTHER DAY ALTERNATLY WITH 30 MG QOD	1/2	0,5000
EVERY OTHER DAY ALTERNATLY WITH 20 MG QOD	1/2	0,5000
ONCE A WEEK	1/7	0,1429
QD (EVERY MORNING)	1	1,0000
SINGLE DOSES	1	1,0000
ALTERNATE DAYS	1/2	0,5000

18.8.1.4 Corticosteroid usage, cumulative and average daily dose

The study protocol defines rules of CS usage during the study. The non-compliance with these rules will be described using data collected in “Concomitant Medications” eCRF form and

subjects' compliance with CS usage rules checked during the medical review and protocol deviation process (i.e. subjects with PD code = PDEV52e).

According to protocol secondary criterion the following criteria will be summarized:

- Cumulative prednisone-equivalent dose (mg) from baseline visit until end of 52-week treatment period. If one subject does not receive any CS between baseline and end of treatment period then his cumulative dose will be set to 0 mg.

Cumulative dose [mg] = sum of (dose per administration * daily dosing frequency * Duration),

with:

- Sum of () = sum of all CS recorded in Concomitant Medication eCRF form, from baseline visit until the end of 52-week treatment period
- Duration = End CS dose date during treatment period – Start CS dose date + 1
- Daily dosing frequency using frequency conversions (See [Table 49](#) and [Table 50](#)).

As CS usage has to be restricted to the period between screening visit and end of treatment period, the following specific rules will be applied only for the calculation of cumulative prednisone-equivalent dose:

- Start CS dose date:
 - If start dose date is before screening date, baseline visit date will be considered as the start date for duration calculation.
 - If start dose date is after end of treatment period, CS will not be considered for duration calculation.
- End CS dose date:
 - If end is missing or after date of last IMP dose + 14 days or CS ongoing, the end CS dose date will be imputed by the last IMP dose date + 14 days for duration calculation. If last IMP dose is missing then end dose date will not be imputed and duration will not be calculated (patient not treated not taken into account in the analysis).
 - If end CS dose date is before baseline date, CS will not be considered
- Average daily steroid dose (mg) from baseline visit until end of treatment period. If one subject does not receive any CS between screening and end of treatment period then his average daily dose will be set to 0 mg.
 - Average daily dose [mg] = $\left(\frac{\text{Cumulative dose [mg]}}{\text{Duration}} \right)$
 - For completers, Duration = Week 52 date – baseline visit date + 1
 - For discontinuers, Duration = Last IMP dose date + 14 – baseline visit date + 1

- If one subject does not receive any CS between baseline and end of treatment period then his daily dose will be set to 0 mg and change from screening value will be equal to 0 mg.
- Prednisone-equivalent daily dose [mg] by visit:
 - The prednisone-equivalent daily dose at visit X is calculated only if visit X is performed during treatment period (date of visit X \leq last treatment intake + 14 days).
 - At a scheduled visit, prednisone-equivalent CS daily dose is equal to the dose the subject is on at the scheduled visit. If several CS are taken at the same scheduled visit then all CS doses should be added. If a prednisone-equivalent CS dose stopped/changed at the scheduled visit date (Week X visit date), then the prednisone-equivalent CS dose started before (Week X visit date - 1 day) will be considered as the CS daily dose for that visit.
 - CS dose taken between two scheduled visits will not be taken into account in calculation of the scheduled-visit dose.
 - For subjects who completed the treatment period, CS dose that started on or after end of treatment will be excluded from the calculation.
 - All comparisons will be done compared to CS dosing at baseline. CS dosing at baseline is defined at CS dose taken the day of baseline visit (day 1). If patient did not receive any CS at baseline then CS dose is set to 0 mg.
 - For defining CS sparing effect endpoint (i.e. sustained reduction by W41 to Week 52), the derivation of prednisone-equivalent CS daily dose will be repeated at Week 40 scheduled visit using a different rule. If a prednisone-equivalent CS dose stopped/changed at the Week 40 scheduled visit date (Week 40 visit date), then the prednisone-equivalent CS dose started after (Week 40 visit date + 1 day) will be considered as the CS daily dose for that visit. Sustained reduction by Week 41 will be then programmed by checking that CS reduction is maintained between this new post-Week 40 (=Week 41) visit and Week 52 visit (i.e. CS dose at Week 52 is less or equal than CS dose at Week 41). The associated conditions related to CS sustained reduction (i.e. CS dose \leq 7.5 mg/day and \leq Day 1 CS dose, CS dose reduction from baseline \geq 25% and CS dose \leq 7.5 mg/day) will be checked for Week 41, 44, 48 and 52 visits.

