The compliance will be computed using the number of kits dispensed as well as the number of tablets returned. Compliance with treatment will be tabulated by treatment group from first intake in LTE to last intake during LTE period and also presented within categories, as for the 52-week treatment period.

The first kit dispensed in LTE treatment period is at Week 52 visit for subjects who rolled over directly from 52-week treatment to LTE.

LTE analysis: Overall period (i.e. 52-week treatment period + LTE)

Overall compliance will be presented on LTE SAF only on subjects who received evobrutinib 50 mg BID during the 52-week treatment period and continue with the same dose of evobrutinib during LTE period.

Overall compliance with treatment is defined using the formula below:

$$\text{Compliance with treatment} = 100 \times \left[\left(\frac{N_1}{5 \times N_2} \right) + \left(\frac{N_3}{4 \times N_4} \right) \right] / 2$$

where

- N_1 = number of tablets given minus number of tablets returned over N_2 days for the 52-week treatment period
- N_2 = number of days between treatment start and treatment termination visit for the 52-week treatment period
- N_3 = number of tablets given minus number of tablets returned over N_2 days for the LTE treatment period
- N_4 = number of days between treatment start and treatment termination visit for the LTE treatment period

Compliance with treatment will be tabulated from first intake to last intake of the study and also presented within categories, as for the 52-week treatment period.

Subject data listings:

For each analysis, the following listings will be provided:

- listing of kit numbers with date of dispense, and number of tablets returned (from BATCH).
- listing of start/end dates with number ingested tablets (from EXPOSUREDT).
- listing with exposure time, cumulative dose, and compliance.

14 Endpoint Evaluation

For all efficacy endpoints:

- Analysis visits will be used (as detailed in Section 9.7 and Appendix 18.11).
- Baseline definition from Section 9.5 should be applied.
- Statistical tests of the two-primary and key secondary efficacy endpoints entering the hierarchical testing procedure (see section 14.1.2.4) will be conducted at a one-sided α level of 0.025. The one-sided p-values and the two-sided 95% CIs will be presented as well as a note on how to interpret correctly the two-sided 95% CIs by considering appropriately the accurate boundary of the interval.

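### Average daily steroid dose for completers counts dosing to last IMP dose + 14 days but divides by days to Week 52 only; at constant dose this overstates it by about 3.8%

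*SAP*

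**What the plan says.** All the rules are in SAP Appendix 18.8.1.4 unless noted.

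- **Stated period of the cumulative dose:** "Cumulative prednisone-equivalent dose (mg) from baseline visit until end of 52-week treatment period". The sum covers "sum of all CS recorded in Concomitant Medication eCRF form, from baseline visit until the end of 52-week treatment period".
- **Stated aim of the date rules:** "As CS usage has to be restricted to the period between screening visit and end of treatment period".
- **End-date rule for the cumulative dose:** "If end is missing or after date of last IMP dose + 14 days or CS ongoing", then "the end CS dose date will be imputed by the last IMP dose date + 14 days for duration calculation". Completers are not excepted.
- **Average daily dose:** cumulative dose divided by Duration.
- **Duration, completers:** "For completers, Duration = Week 52 date – baseline visit date + 1".
- **Duration, discontinuers:** "For discontinuers, Duration = Last IMP dose date + 14", less the baseline visit date, plus 1.

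Three other places bear on this. Section 13.1 defines the last dose, for exposure, as the last IMP administration in the 52-week period; the steroid appendix does not repeat that definition. Section 18.8.1.1 drops steroids that start on or after end of treatment. Section 13.2 states: "The first kit dispensed in LTE treatment period is at Week 52 visit for subjects who rolled over directly from 52-week treatment to LTE".

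**The concern.** A time-averaged dose is meaningful only if dose and days are counted over the same period. For discontinuers they are. For a completer whose steroid continues past Week 52, up to 14 further days of dosing can enter the numerator when the last IMP dose is at Week 52, and no matching days enter the denominator.

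The same end-date rule also sits badly with the stated period of the cumulative dose. Unless the 52-week treatment period is meant to include a 14-day tail, the rule goes past it. For completers who roll over directly, those days fall in the open-label LTE, where former placebo subjects take evobrutinib (Table 6).

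At stake are the accuracy of a descriptive summary and a clear definition of the cumulative dose, which is a secondary endpoint compared with placebo by a Wilcoxon test in Section 14.3.5.

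**Working it through.** The SAP gives no worked figure for average daily dose, so there is none to reproduce. The check is a day count from its formulas.

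**Inputs**
- Week 52 is Day 365 (Section 18.11, Table 51). With baseline on Day 1, the completer denominator is 365 − 1 + 1 = 365 days.
- The numerator ends at last IMP day + 14 for an ongoing steroid (18.8.1.4).
- The last IMP day of a completer is an assumption: Day 365, varied from Day 351 to Day 379.

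**Constant dose, steroid ongoing.** Relative error = (last IMP day + 14) / 365 − 1.

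| Last IMP day | Days in numerator | Error in average |
|---|---|---|
| 351 | 365 | 0% |
| 358 | 372 | 1.9% |
| 364 | 378 | 3.6% |
| 365 | 379 | 3.8% |
| 366 | 380 | 4.1% |
| 372 | 386 | 5.8% |
| 379 | 393 | 7.7% |

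At 10 mg/day and last dose on Day 365, the cumulative dose is 10 × 379 = 3,790 mg, against 10 × 365 = 3,650 mg to Week 52. The reported average is 3,790 / 365 = 10.38 mg/day.

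**Dose changed once, steroid ongoing, last IMP dose on Day 365.** With dose d1 before day s and d2 from day s, the excess is 14 × d2 and the total to Week 52 is d1(s − 1) + d2(365 − s + 1).

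- Taper from 20 to 7.5 mg on Day 85: 105 / (1,680 + 2,107.5) = 2.8%.
- Increase from 10 to 20 mg on Day 183: 280 / (1,820 + 3,660) = 5.1%.
- Increase from 5 to 20 mg on Day 337: 280 / (1,680 + 580) = 12.4%.
- Steroid stopped before Week 52: 0%.

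**Discontinuer, constant dose, last IMP dose on Day 180.** Both numerator and denominator run to Day 194: 194 / 194 = 1, so there is no error.

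**After alignment.** With both cut at Week 52, 3,650 / 365 = 10.00 mg/day. With both run to last dose + 14, 3,790 / 379 = 10.00 mg/day.

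**The case against.** The best defence is that the SAP has a 14-day convention. Section 9.7 accepts assessments up to 14 days after last exposure, and 18.8.1.4 counts a visit as within the treatment period if it falls no later than 14 days after last intake. On that reading the cumulative dose ends where intended, and its stated period is only loosely worded. This is a fair answer to the point about the cumulative dose. It does not rescue the average: if the 14 days belong to the period, they belong in the completer denominator too.

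It can also be said that little depends on this. Average daily dose appears only in the appendix, not in Table 1 or among the Section 14.3.5 endpoints, and has no test. In the tested cumulative dose, the 14-day rule applies to completers and discontinuers alike, and Section 14.3 treats the p-values as nominal. All of this stands and limits the severity.

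Four stronger readings are tempting but not supported:

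- **That 3.8% is a ceiling.** It is the constant-dose value for a last dose on Day 365; the working shows both lower and higher values.
- **That subjects are pushed over the 7.5 mg/day limit.** That limit is applied to baseline dose (Table 12) and to visit doses (Sections 14.3.1 and 14.3.5), which have their own derivation. No category is applied to the average.
- **That every completer's extra days are LTE days.** The LTE is optional (Section 10.1), and some subjects have a gap of at least two weeks before it (Section 9.7). Steroids newly started on or after end of treatment are excluded.
- **That the arms cannot be compared.** Distortion between arms requires them to differ in completion or in end-of-period dose. Under the constant-dose case, a 10-point difference in completion moves the comparison by about 0.1 × 3.8% = 0.4%, or 0.04 mg/day at 10 mg/day.

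**Conclusion.** The inconsistency is real and confined to the average daily dose of completers whose steroid is carried to last IMP dose + 14 days. Whichever end of the treatment period is intended, the ratio as written covers two different periods.

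The size is about 3.8% under two assumptions: a constant ongoing dose, and a last IMP dose on Day 365, which the appendix does not fix. The contradiction with the stated period of the cumulative dose is conditional: it disappears if that period is meant to include the 14-day window, but the SAP should then say so.

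The impact is minor. No primary or key secondary result is touched, and no test uses the average.

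**What to change.** Use the same end date in numerator and denominator for every subject. There are two ways:

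1. Add the 14 days to the completer denominator, so that it has the form already used for discontinuers. This changes only the descriptive average and leaves the tested cumulative dose as it is.
2. Apply one stated cut-off to all subjects in both measures, such as the earlier of last 52-week-period IMP dose + 14 days and the Week 52 date (the scheduled date where there was no Week 52 visit). This also removes the days after Week 52, but it changes the cumulative dose.

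Cutting completers' cumulative dose at Week 52 while discontinuers keep an unconditional 14-day extension should be avoided. It would make the Wilcoxon-tested endpoint depend on completion status in a way that it does not now.

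With either choice, state that last IMP dose means the last dose of the 52-week period, as Section 13.1 does for exposure, and make the stated period of the cumulative dose agree with the cut-off.

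The cost is one line of derivation and one or two SAP sentences. Because the primary analysis results had already been reviewed (Section 6.4), any affected outputs would also need re-running, or the discrepancy disclosing in the CSR.

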14.3.1 Disease Activity Endpoints

The following secondary endpoints to be analyzed on mITT analysis set are summarized in [Table 19](#). LLDAS is defined in [Appendix 18.1.7](#).

For SRI-4 and SRI-6 response endpoints as well as LDA status and LLDAS, the primary analysis method applied to the two-primary endpoints ([Section 14.1.2.1](#)) will be performed.

In addition, for LDA and LLDAS endpoints in [Table 19](#), the number and percentage of subjects with response or non-response will be summarized over time (by visit), using similar imputation rules as applied for the Week 52 timepoint.

Table 19 : Disease Activity Endpoints

Endpoint	Analysis method	Data Handling Notes

 • SRI-6 response at Week 52, in the serologically active subgroup • SRI-4 Response at Week 52 with a Sustained Reduction of OCS Dose to 7.5 milligrams prednisone-equivalent per day or less (≤ 7.5 mg/day) and less than or equal to (\leq) Day 1 dose during Week 41 Through Week 52, in all subjects • SRI-6 Response at Week 52 with a Sustained Reduction of OCS Dose to 7.5 milligrams prednisone equivalent per day or less (≤ 7.5 mg/day) and less than or equal to (\leq) Day 1 dose during Week 41 Through Week 52, in the HDA subgroup • SRI-4 Response at Week 52 with a Sustained Reduction of OCS Dose to 7.5 milligrams prednisone equivalent per day or less (≤ 7.5 mg/day) and less than or equal to (\leq) Day 1 dose during Week 41 Through Week 52, in the serologically active subgroup 	Same as the Primary Method in Table 17	Same as the Primary Method in Table 17

 • LDA status, defined by SLEDAI-2K ≤ 2 at Week 52 • LDA, defined by clinical SLEDAI-2K (SLEDAI-2K excluding anti-dsDNA and low complement parameters) ≤ 2 at Week 52 • LLDAS at Week 52 	Same as the Primary Method in Table 17	Same as the Primary Method in Table 17

In order to determine whether the subject had a sustained reduction of OCS Dose to ≤ 7.5 mg/day and \leq Day 1 dose during Week 41 Through Week 52, the daily dose of CS will be calculated for each analysis visit from Week 41 to Week 52, according to Appendix 18.8. If the condition is met for all days during this period, the subject will be considered as having a sustained reduction of OCS Dose.

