14.3.5 Corticosteroid usage over time

CS usage over time will be analyzed on the mITT set using data collected in “Relevant Previous Medications Details” and “Concomitant Medications” eCRF Forms.

Only CS taken at baseline or after will be taken into account. Any CS with an end date before screening date will not be taken into account in the following analysis.

General rules, missing data handling, conversions and cumulative dose is defined in Appendix 18.8.

The following endpoints will be described for statistical analysis:

- Clinically meaningful reduction in CS dose from Baseline, defined by:
 - A reduction of daily prednisone-equivalent CS dose $\geq 25\%$ to a dose of ≤ 7.5 mg/day by Week 40 + 1 day (i.e. Week 41) and sustained through Week 52

AND

- No new BILAG A organ domain scores and no more than one new BILAG B organ domain score during Weeks 40 + 1 day (i.e. Week 41) through 52.

Subjects withdrawing from treatment before Week 40 or with missing data at Week 40 will be considered as non-responders. The analysis will be performed on the mITT subjects whose CS dose is greater than or equal to 7.5 mg at baseline.

- Change from Baseline to Week 52 in prednisone-equivalent CS daily dose.

Summary statistics for absolute value, CFB and percent CFB by visit during treatment period in prednisone-equivalent CS daily dose will be provided.

- Reduction by visit, from Baseline to Week 52, in prednisone-equivalent CS daily dose of zero to < 25%, 25% to 50%, > 50%, or an increase.

The same table will be produced with the following categories of prednisone-equivalent CS daily dose at Week 52: ≤ 6 mg, > 6 - 7.5 mg, > 7.5 – 10 mg, > 10 – 20 mg, > 20 – 30 mg and > 30 mg. The proportions are based on the observed subjects as the denominator.

- Cumulative prednisone-equivalent CS dose from Baseline until completion of the Treatment Period (absolute value only) will be described using summary statistics.

Cumulative prednisone-equivalent CS dose will be compared between placebo arm and evobrutinib arms with a pairwise non-parametric Wilcoxon rank sum test.

[figure not shown]
All CS doses will be listed for each subject and flagged for any doses not taken into account in calculation of the scheduled-visit dose (e.g. dose taken between two scheduled visits or dose with missing information). Subjects non-compliant with protocol rules on CS usage will be listed based on protocol deviation data (i.e. all subjects with PD code = PDEV52e).

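### The visit-based check of sustained steroid reduction contradicts the plan's all-days rule, and the Wilcoxon test of cumulative steroid dose ignores time on study

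*SAP*

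**What the plan says.** **Sustained reduction.** For the three SRI-plus-oral-steroid endpoints, SAP section 14.3.1 says: "If the condition is met for all days during this period, the subject will be considered as having a sustained reduction of OCS Dose". The sentence before it says that "the daily dose of CS will be calculated for each analysis visit from Week 41 to Week 52", and refers to Appendix 18.8 for the derivation. Section 18.8.1.4 then sets the visit dose to what the subject is taking at the visit, with the exclusion "CS dose taken between two scheduled visits will not be taken into account in calculation of the scheduled-visit dose". It judges maintenance by whether "CS dose at Week 52 is less or equal than CS dose at Week 41", and says that the dose conditions "will be checked for Week 41, 44, 48 and 52 visits". The same derivation serves the clinically meaningful reduction endpoint of section 14.3.5.

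**Cumulative dose.** Section 14.3.5 states: "Cumulative prednisone-equivalent CS dose will be compared between placebo arm and evobrutinib arms with a pairwise non-parametric Wilcoxon rank sum test". Section 18.8.1.4 sums all recorded systemic steroid use and ends any course that is ongoing, or that runs past that point, at the last study dose plus 14 days. It also defines an average daily dose, but the plan names no between-arm test of it.

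**Drop-out and start dates.** For the clinically meaningful reduction endpoint, section 14.3.5 says: "Subjects withdrawing from treatment before Week 40 or with missing data at Week 40 will be considered as non-responders". For cumulative dose, section 18.8.1.4 says: "If start dose date is before screening date, baseline visit date will be considered as the start date for duration calculation".

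**The concern.** A programmer cannot follow both 14.3.1 and 18.8.1.4. Following the appendix delivers a weaker endpoint than the one defined: a steroid course that starts and ends between two visits is never seen, and the subject is counted as a steroid-sparing responder. This touches the three SRI-plus-oral-steroid endpoints and the clinically meaningful reduction endpoint.

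The Wilcoxon test has a different fault. A subject who leaves at Week 12 has a smaller total than a completer on the same daily dose, simply because the clock stopped. If drop-out differs between arms, the test mixes drop-out with steroid use, and a nominally significant result may reflect only the former. Both results feed the steroid-sparing account in the study report.

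**Working it through.** The plan states no power or effect figure for the steroid endpoints, so there is none to reproduce. The checks apply its own formulas.

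**1. Between-visit course**
- Inputs: Week 40 is Day 281 and Week 52 is Day 365 (SAP Table 51), so the period is 365 − 281 = 84 days. The limit is 7.5 mg/day (14.3.1).
- Illustrative subject (assumed doses): 5 mg/day, replaced by 40 mg/day for 7 days between the Week 44 and Week 48 visits.
- Visit doses at the four checks: 5, 5, 5, 5 mg. Week 52 is not above Week 41. Result under 18.8.1.4: sustained.
- Result under 14.3.1: not sustained, because 7 days exceed the limit.
- Mean over the period: (5 × 77 + 40 × 7) / 84 = 665 / 84 = 7.9 mg/day.

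**2. Effect of leaving early on cumulative dose**

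Formula (18.8.1.4): dose × days, ending at last study dose + 14 days. At a constant 10 mg/day:

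| Last study dose | Days counted | Cumulative dose |
|---|---|---|
| Day 364 (completer) | 378 | 3780 mg |
| Week 40 | 294 | 2940 mg |
| Week 26 | 196 | 1960 mg |
| Week 12 | 98 | 980 mg |

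The average daily dose under 18.8.1.4 is 10.0 mg for each discontinuer. For the completer it is 3780 / 365 = 10.36 mg, because the numerator runs to last study dose + 14 days while the denominator stops at Week 52.

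**3. Wilcoxon test with identical daily doses in both arms, two-sided 0.05**

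The plan gives no drop-out rate by arm, so all rates here are assumed. It plans for 5% overall (8.2.1) and mentions a potentially higher rate (section 7). Two sets of assumptions were simulated, each with 20% of subjects at 0 mg and the rest log-normal with median 8 mg/day:
- Set A: 115 per arm, log-SD 0.5, leaving uniformly between Days 28 and 350; 3000 or 4000 runs per setting.
- Set B: 108 per arm (8.2.1), log-SD 0.6, leaving uniformly over 52 weeks; 4000 runs per setting.

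| Drop-out, placebo vs drug | Set | Rejection, cumulative dose |
|---|---|---|
| 20% vs 20% | A | 5.0% |
| 20% vs 20% | B | 4.1% |
| 5% vs 10% | A | 6.1% |
| 20% vs 30% | B | 7.8% |
| 15% vs 30% | A | 10.3% to 10.6% |
| 30% vs 15% | A | 11.4%, almost all favouring placebo |
| 20% vs 40% | A | 15.0% to 15.8% |
| 20% vs 40% | B | 14.4% |
| 40% vs 20% | B | 15.4%, almost all favouring placebo |

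The ranges in set A are repeat runs. Testing dose per day on study in the same data gives 4.3% to 5.5% in every set B setting and stays near 5% in set A.

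**4. Smaller gaps**
- The clinically meaningful reduction must last through Week 52, but the non-responder rule stops at Week 40. A visit dose exists only up to 14 days after the last intake, so a Week 45 leaver has no Week 52 dose, and 14.3.5 does not say what follows.
- The start date is reset to baseline only for a steroid begun before screening. One begun between screening and baseline, and still running, keeps its own start date. At 10 mg/day, each such day adds 10 mg to a total defined as starting at baseline.

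**The case against.** Several points on the other side stand.

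- **The two faults affect different endpoints.** A reader might infer that both run through every steroid endpoint and flatter the drug. They do not. Cumulative dose sums all recorded courses, so bursts are counted there. In the SRI composites, Table 19 applies the primary data handling, so a missing Week 52 response is non-response and drop-out counts against the arm.
- **The direction is not fixed.** The cumulative-dose error follows the arm with more drop-out, which may be placebo. With equal drop-out there is no inflation.
- **Some bursts will already fail.** SRI criterion 4 (14.1.1) makes committee-determined prohibited medication a non-response. Whether a given course qualifies depends on the protocol and the committee charter, which are not at hand. This route need not catch every course, and the clinically meaningful reduction endpoint has no such condition.
- **Four of 84 days overstates the gap.** The visit dose is the regimen the subject is on, so a course spanning a visit is caught. Only courses that fall between visits escape.
- **Leavers between Weeks 40 and 52.** A reader might infer that they pass. The plan is silent, and failure for want of a Week 52 dose is a natural reading.
- **All days may have meant all visits**, since 14.3.1 derives the dose by visit. That may have been the intention, but it is not what the sentence says. Excluded doses are flagged in a listing (14.3.5), which discloses them without changing the classification.

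**Conclusion.** Two points hold. First, 14.3.1 and 18.8.1.4 contradict each other on sustained reduction, and the visit rule can class a subject averaging 7.9 mg/day as sustained at or below 7.5 mg/day. How often this happens depends on the frequency of between-visit courses, which the plan does not give. Second, the Wilcoxon test of cumulative dose does not hold its 5% level when drop-out differs by arm: about 10% at 15% versus 30% and about 15% at 20% versus 40%. The mechanism comes from the plan; the sizes rest on the assumed drop-out rates and dose distribution, and at 5% versus 10% the inflation is slight (6.1%).

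The Week 40 cut-off is an unstated case in one endpoint. The pre-baseline days precede treatment and add noise rather than bias between arms.

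A reader might infer that the trial's main conclusions are at risk. They are not: these are other secondary endpoints with nominal p-values (14.3), outside the testing hierarchy of 14.1.2.4.

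**What to change.** 1. Reconcile 14.3.1 with 18.8.1.4: build a day-by-day prednisone-equivalent dose from the recorded start and stop dates, and apply the all-days condition of 14.3.1 from Week 41 to Week 52. Use the same record for the clinically meaningful reduction endpoint.
2. Keep cumulative dose as a descriptive endpoint and move the between-arm test to average daily dose, with numerator and denominator covering the same period for completers as well as discontinuers.
3. For the clinically meaningful reduction endpoint, extend the non-responder rule to any withdrawal before Week 52.
4. Truncate steroid start dates at the baseline visit, not only those before screening.

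The cost is programming on data already collected. Sustained-response rates may fall slightly. Version 4.0 of the SAP follows review of the primary analysis and the study's termination, so any re-derived 52-week result should be labelled as re-derived after that analysis and shown beside the result under the existing rule.

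### Sustained steroid reduction is defined over all days from Week 41 to Week 52 in Section 14.3.1 but programmed from four visit-day doses in Appendix 18.8.1.4

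*SAP*

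**What the plan says.** Section 14.3.1 covers three composites: SRI-4 in all subjects, SRI-6 in the high disease activity subgroup and SRI-4 in the serologically active subgroup, each combined with a sustained oral steroid dose of at most 7.5 mg/day and no higher than the Day 1 dose from Week 41 through Week 52. It gives the derivation in two consecutive sentences. First, "the daily dose of CS will be calculated for each analysis visit from Week 41 to Week 52, according to Appendix 18.8". Then, "If the condition is met for all days during this period, the subject will be considered as having a sustained reduction of OCS Dose".

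Section 14.3.5 defines a fourth endpoint, the clinically meaningful corticosteroid reduction. It is a reduction of at least 25% to at most 7.5 mg/day, reached "by Week 40 + 1 day (i.e. Week 41) and sustained through Week 52", together with a BILAG condition over the same weeks. This section does not use the all-days wording.

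Appendix 18.8.1.4 sets the dose used for both. "At a scheduled visit, prednisone-equivalent CS daily dose is equal to the dose the subject is on at the scheduled visit"; where the dose stopped or changed on the visit date, the dose from the day before is used. "CS dose taken between two scheduled visits will not be taken into account in calculation of the scheduled-visit dose." For the sustained endpoints it adds a re-derived dose just after the Week 40 visit, called Week 41. It tests maintenance by whether the "CS dose at Week 52 is less or equal than CS dose at Week 41", and says that both sets of dose conditions "will be checked for Week 41, 44, 48 and 52 visits".

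**The concern.** A dose known on four visit days cannot show that a limit held on every day between them. A subject who takes a course above 7.5 mg/day that starts and stops between the Week 44 and Week 48 visits fails the criterion in Section 14.3.1 but passes the check in Appendix 18.8.1.4. Two programmers, each following one of the two passages, would score that subject differently.

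The SAP expects such doses. Section 14.3.5 names steroid taken between two scheduled visits as a category to be flagged in the listing, and Appendix 18.8 has rules for single-day administrations and conversion factors for one-off doses. They enter the cumulative dose, but no rule lets them change sustained status. What is at stake is the meaning of the steroid-sparing claim. Section 7 also drops another steroid endpoint because the clinically meaningful reduction is judged sufficient, so more of that evidence rests on this derivation.

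**Working it through.** The SAP gives no figure to reproduce here, so the check counts days.

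**Inputs.** Table 51 (Appendix 18.11) gives nominal days: Week 40 = Day 281, Week 44 = Day 309, Week 48 = Day 337, Week 52 = Day 365. Week 41 is the Week 40 visit plus one day, Day 282. Course lengths and uniformly distributed start days are assumptions; the SAP gives neither.

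**Coverage.** Days 282 to 365 are 365 − 282 + 1 = 84 days. Four are checked, leaving 80 unchecked: 80/84 = 95%.

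**Longest unseen course.** The gaps between checked days are Days 283–308 (26 days), 310–336 (27 days) and 338–364 (27 days). A course of up to 27 days can fit in a gap; one of 28 days or more within the window always meets a checked day.

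**Share of start days that escape.** For a course of L days lying within Days 283–365:
- possible start days: 83 − L + 1 = 84 − L
- start days touching no checked day (L up to 27): (26 − L + 1) + 2 × (27 − L + 1) = 83 − 3L

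In a stricter variant the day before the Week 44, 48 and 52 visits also counts as checked, because of the rule for doses changed at the visit. The gaps become 25, 26 and 26 days, and the escaping starts are 80 − 3L (none at 27 days or more).

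| Course length (days) | Possible starts | Escape, visit days only | Escape, stricter variant |
|---|---|---|---|
| 3 | 81 | 74 (91%) | 71 (88%) |
| 7 | 77 | 62 (81%) | 59 (77%) |
| 10 | 74 | 53 (72%) | 50 (68%) |
| 14 | 70 | 41 (59%) | 38 (54%) |
| 21 | 63 | 20 (32%) | 17 (27%) |
| 27 | 57 | 2 (4%) | 0 |
| 28 | 56 | 0 | 0 |

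If the course must end by Day 364, there are 83 − L possible starts. The visit-day shares for 3, 7, 10 and 14 days are then 74/80 (93%), 62/76 (82%), 53/73 (73%) and 41/69 (59%).

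**Direction.** Every dose that the visit rule inspects is a dose on some day in the window. With the Week 52 versus Week 41 comparison kept the same under both rules, a subject who meets the limits on all days also meets them at the checked visits, but not the reverse. The visit rule can therefore add responders relative to the all-days rule and cannot remove any.

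**The case against.** The strongest reply is that Section 14.3.1 itself sends the derivation to Appendix 18.8 by analysis visit, so the all-days sentence may be loose wording for all those visits. On that view the between-visit exclusion is open and deliberate, and rewording Section 14.3.1 would settle the matter. This does not remove the conflict, because the sentence as written sets a requirement that visit-day doses cannot establish. It does show that the wording could be reconciled in either direction.

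Several other points stand:
- The all-days wording applies to the three composites only. The clinically meaningful reduction is reached through the shared derivation, not through Section 14.3.1.
- A subject whose steroid component is wrongly scored need not be a responder. The composites also carry the SLEDAI-2K, PGA and BILAG conditions and adjudicated treatment failure. The fourth endpoint carries its BILAG condition, though no adjudication criterion is stated for it. The adjudication charter and the protocol's steroid rules are not shown.
- Between-visit steroid is not lost: it is listed, flagged and counted in the cumulative dose, which is compared between arms.
- A day-level rule is more exposed to partial dates. Appendix 18.8.1.2 moves a missing start day to the first of the month and a missing end day to the last, and concurrent doses are added, so an artificial overlap could breach the limit.

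A reader might infer that the missed courses fall mainly in the arm with worse disease control and so pull the arms together. The documents do not support that: they give no frequency, purpose or distribution of short courses by arm. Nor are the shares in the table error rates for the endpoint. They are conditional on a course occurring, lying in the window and having the assumed length.

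**Conclusion.** The contradiction between Section 14.3.1 and Appendix 18.8.1.4 is real. The programmed rule inspects 4 of 84 nominal days and cannot see a course of up to about 27 days that lies between checks. The 27-day limit rests on nominal visit days and would shift with actual visit dates. Relative to the all-days rule the effect on responder counts goes one way, upwards. Its size cannot be estimated from the documents, and neither can any bias between arms.

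This should be fixed but is not critical. The endpoints are other secondary endpoints outside the hierarchical testing procedure; the composites have nominal p-values, and no between-arm test is specified for the clinically meaningful reduction. A reader should not infer that the primary or key secondary tests, their error control or the sample size are affected.

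**What to change.** Reconcile the two passages:

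1. For the three SRI composites, build the prednisone-equivalent dose for every day from Week 40 + 1 day to the Week 52 visit from the dated steroid records, and require the limits on each day, as Section 14.3.1 states.
2. Apply the same derivation to the clinically meaningful corticosteroid reduction, for consistency.
3. State that the between-visit exclusion applies only to by-visit dose summaries.
4. Flag subjects whose day-level status depends on an imputed start or stop date.

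Version 4.0 was written after the primary analysis had been reviewed and the study terminated, so the day-level result should not silently replace the existing one. Report the two side by side, label the day-level result post hoc, as Section 4 requires for unplanned analyses, and state which rule produced each.

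The cost is SAP wording and one day-level derivation; the start and stop dates are already processed for the cumulative dose. The downsides are probably slightly fewer responders and some possible false failures from imputed date overlaps.
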